### **2.3 Rationale for study design**

This study will adopt a case study approach. Case studies are appropriate for illuminating decisions, including why decisions were taken, how they were implemented and what the consequences were. Case studies are also the preferred method for ‘how’ and ‘why’ questions [19, 20]. The study will include predominantly qualitative data collection methods, including community consultations, observations, FGDs and IDIs. However, the study will also include collection of quantitative process data and recruitment of a cohort to better evaluate the two models of secondary distribution.

### **3. Roles and responsibilities for implementation**

---

This research protocol focuses on the research activities being carried out by trained researchers at Zambart. The distribution of HIVST will not be done by the research team, rather by separate teams of implementers and Ministry of Health (MOH) staff. Society for Family Health (SFH) and MOH will lead the implementation of the four models of HIVST kit distribution in the second phase of the STAR initiative, with Zambart leading implementation of one model and responsible for all research activities.

Table 1 summarises the distribution models for which case studies are planned, see also appendix 1 for a more detailed description of the models.

1. The distribution of HIVST will include the following inputs, from SFH and/or Zambart:  
Training of an existing cadre of health care workers (employed by MOH), CHiPs or SFH distributors on how to offer HIVST to individuals, including for secondary distribution. This will include training on basic HIV information, HIVST information (how to demonstrate the use of HIVST and read the results), HIV related social harms, services available for individuals who experience social harms and process of linking such individuals to organisations that offer help.
2. Coordinating with MoH during the implementation period and ensuring that HIVST kits are distributed in line with the Zambian HIV testing guidelines.
3. Distribution of HVST kits in the MoH health facilities and the catchment area of the facility.
4. Collection of basic process data information during HIVST distribution.
5. Promotion and social marketing of HIVST (led by SFH) through different channels, including fliers, posters and drama performances in the community. Public address systems will also be used to create awareness about HIVST.
6. For the workplace model, SFH will seek permission from senior management personal in charge of the workplace. SFH will also negotiate for time and a private room or space to distribute HIVST kits to the workers.

The main role of Zambart will be to conduct research activities to evaluate the five models of HIVST distribution. Individuals will come in contact with the researcher after they have been offered an HIVST kit and whether they accept or not.

All individuals, regardless of whether they take an HIVST kit for primary or secondary distribution, will be informed of the follow-up services available to them and their partners (if applicable) at the health facility. Individuals will be informed that the HIVST is a screening test, such that if the test is reactive they will need to attend the health facility for confirmatory testing. Confirmatory testing will be conducted using Determine HIV™ and SD Bioline™ in line with Zambian HIV testing guidelines [3]. Individuals will also be informed that a non-reactive test does not require any confirmatory testing, but that they should return to the health facility to link to prevention services, including VMMC or to obtain a supply of condoms.

For the secondary distribution models, staff training will include additional steps to ensure that index patients understand how to demonstrate the use of the HIVST to their partner, and to communicate the next steps to be followed for a reactive or non-reactive result. SFH distributors will request that index patients collecting a secondary distribution HIVST kit for their partners to inform their partner about the availability of HIV-related follow-up services, including confirmatory testing where the HIVST is reactive.

[figure not shown]
## 4. Methods

### 4.1 Study population and location

The study population will include individuals aged 16 years or older (the age of consent for HIV testing in Zambia), who access health facility services where HIVST kits are being distributed. The study location is five peri-urban communities in Lusaka, Zambia. These communities vary in population size from 41,825 to 106,000 individuals. In each of the communities, the facility-led model will be implemented in the public health facility and the community-led model will be implemented in all facility catchment areas. Facility-level distribution will utilize the existing systems of service delivery. Distribution of HIVST will be done within the facility and during outreach programs. The VMMC model will target potential VMMC clients within the communities surrounding the clinic during facility-led outreach activities.

The selection criteria of the communities included having a health facility that offers HIV ST services, presence of an ART clinic and a catchment population size of more >40,000. (Figure 1).

**Figure 1. Map indicating location of study sites**

SFH intends to distribute HIVST through workplaces such as the banks, mobile phone providers, mines, governmental and quasi-governmental organisations, manufacturing companies and others. These workplaces may not be located in the five communities. The SFH

team is currently mapping and assessing the workplaces where HIVST distribution will be done. For this study, we will conveniently and purposively sample two workplaces from those where SFH will distribute HIVST.

**Table 2: Summary of data collection methods for all distribution models**

Case study numbe r	Model of HIVST distributio n	Data collection method			Participants and recruitment
		Quantitative	Qualitative	Economic	
1	VMMC		Community consultations Physical/social community maps and 4 stakeholder discussions 18 IDIs & 3 FGDs with approx. 140 participants Observations	N/A, already costed	VMMC clients aged 16 years and above (1 FGD, 6 IDI)
2	Facility- and community -led	Process data		Document reviews and process data Observations such as time and motion. Costing data abstraction sheet	All individuals of the general population aged 16 years and above (2 FGDs, 6 IDI)
3	Workplace				All individuals aged 16 years and above (1 FGD, 6 IDI)  4 community stakeholder meetings
4	Secondary distribution through ANC	Process data Quantitative cohort with approximately 450 individuals per cohort (900 total)	As above plus Observations Qualitative cohort of 12 participants selected from ANC & HIV testing and treatment services (24 IDI).  8 FGDs with community members/ ANC and ART clients for community perspectives on secondary	Exit interviews Quantitative cohort Document reviews and process data Observations such as time and motion. Costing data abstraction sheet Discussion with providers	Exit Interviews/quantitative cohort- consecutive clients offered HIVST for secondary distribution (approximately 450) Primary partners of cohort who were offered HIVST. 12 individuals purposively selected for qualitative cohort (IDIs) 4 FGDs; 2 IDIs with HCWs
5	Secondary distribution through				Exit Interviews/quantitative cohort - consecutive

Case study numbe r	Model of HIVST distributio n	Data collection method			Participants and recruitment
		Quantitative	Qualitative	Economic	
	HIV testing and treatment services		distribution and 4 IDIs with HCWs.		clients offered HIVST for secondary distribution ( approx. 450) Primary partners of cohort. 12 individuals purposively selected for qualitative cohort (IDIs) 4 FGDs; 2 IDIs with HCWs

## **4.2 Qualitative methods**

Qualitative data collection will begin with implementation of participatory activities through community consultation processes and stakeholder discussion, followed by IDI, FGD, mapping, and observation of HIVST distribution (Table 2). Qualitative data will provide understanding of contextual factors that mediated people's choices and behaviour. The qualitative research will explore the following themes:

1. Social support and social networks (friends, workmates, church, customs, support after testing, attitudes of HCWs)
2. Livelihood options
3. Knowledge of HIV testing and HIVST, and individual attitudes towards HIV testing and HIVST
4. Power relations, social harms and gender-based violence within couple/partners
5. Social effects of HIVST including stigma
6. Location and lay-out of distribution points, including community social and physical features
7. Environmental factors (flooding, disease outbreaks, strikes etc.)
8. Promotion and social marketing

A total of 12 FGDs and 46 IDIs will be conducted (see table 2 for distribution). Both the FGDs and IDIs will be conducted by trained RAs with the help of a Junior and senior social scientist. The Neighbourhood Committee (NHC) members will help to identify appropriate venues within the community. The NHC is a community-based organisation created by an act of parliament to ensure community involvement in the management of health related programmes in the community. The size of the focus groups will be between 8-12 participants. This is the recommended size to ensure interaction between the participants. Focus group discussion and IDI participants will be selected purposively for each distribution model, aiming for a range of ages, men and women, and individuals who accepted or declined an offer of HIVST. The composition of the FGDs is described in section 5.1 (recruitment of qualitative study participants). In addition 4 stakeholder discussions with representatives of community based groups and 15 observations of the mechanisms of distribution and interactions between distributors and clients will be conducted.

Twelve individuals from each of the quantitative cohorts linked to secondary distribution methods (24 in total) will be purposely selected to take part in the Secondary Distribution qualitative cohort. They will be interviewed at two points: at recruitment and follow-up.

### **Community Consultations**

Using a consultative process at the beginning of the study, we will: introduce the study to communities and obtain community buy-in; identify appropriate stakeholders that may later

form the system for identifying and reporting social harms; identify case parameters/boundaries through community views about different aspects of the HIVST distribution models. The latter process will involve discussing with community members some of the contextual factors already identified in this protocol and new ones to set the boundaries of the cases. Contextual factors to be explored include: location and distance to the distribution points or places, stigma (anticipated, enacted and internalised), availability of social support, power relations between partners, social harms including intimate partner violence, knowledge of HIV testing and HIVST, and livelihood options.

Community consultations will be conducted among men, adolescents and young people, women attending ANC, key populations and other community members from the general population prior to the commencement of the study. The consultations will primarily be focussed on getting the perspectives of the community on the proposed HIVST distribution models. Participants will be asked for their views on the ideal components of the models, and the likely mechanisms that will facilitate implementation and change.

Time and process for the consultations will differ from community to community depending on the availability of prior information about each community. Overall, community consultations will be conducted within 7 days. An ideal consultative process is presented below:

### **Community Entry Consultations**

The purpose of this stage is to introduce HIVST to traditional and civic leaders- those who have not heard or are experiencing it for the first time, and to update those who already know about HIVST. The following steps will be followed:

1. Hold meetings with the Neighbourhood Health Committees, Ward Development Committees/Resident Development Committees and Health Facility Management to identify key traditional and civic authorities
2. Meet with traditional and civic leaders/ authority
3. Introduce HIVST / study to community leaders and authorities

### **Community Participatory Assessments**

This stage will primarily focus on mapping stakeholders and potential distribution points in the community using purposely selected community members. Information collected will also be used to review case studies:

1. Use of Participatory Rapid Appraisal (PRA) tools to elicit community views about 1) potential stakeholders 2) possible HIVST distribution points 3) possible implementation mechanisms for distribution models proposed by the study
2. Tools to be used will include physical maps and social maps – the former for places and key features of the community and the latter for key stakeholders
  - a. Map key stakeholders
  - b. Map potential distribution places
  - c. Identify physical features that will facilitate and or hinder 1) distribution of HIVST kits 2) uptake of HIVST 3) linkage to confirmatory testing 4) linkage to care by those who self-test positive.

- d. Identify social features that will facilitate and or hinder 1) distribution of HIVST kits 2) uptake of HIVST 3) linkage to confirmatory testing 4) linkage to care by those who self-test positive.
- e. Identify social and physical features that will facilitate or hinder implementation of secondary distribution models (ANC and HIV+ individuals)

The mapping exercise will be conducted shortly before the commencement of the study to map potential HIVST stakeholders and HIVST distribution models/points. Selected representatives of the community (opinion leaders) will draw community maps and include features of the community that relate to or may impact positively or negatively on HIVST distribution. The exercise will be facilitated in such a way as to enable the community representatives to reflect/relate the features to the distribution models that the study will explore.

### **Stakeholder Meeting**

The meeting is intended to introduce the study to key stakeholders and to ensure inclusiveness of the consultative process:

1. Invite representatives of stakeholders identified above
2. Ensure a broad mix of HIV and non-HIV related stakeholders.
3. Conduct a stakeholder identification review (what stakeholders are missing; ensure that both CBOs and NGOs are included; ensure faith based are included; if the Church is identified as a stakeholder ask for particular groups and organisations within the church that the study can closely relate with)
4. Conduct a ‘quick and dirty’ stakeholder analysis/ranking to obtain views of community members (participants) about the relative importance they attach to the stakeholders that were identified in 3 above. The ranking technique to be used are from the PRA tools which will enable share their knowledge of the community related to HIV testing and thereby promote a bottom up approach [21].

### **Stakeholder Analysis**

This stage will involve collecting information on key stakeholders:

1. Visit key stakeholders identified from the stakeholder meeting and conduct a detailed stakeholder analysis
2. Features of the stakeholder analysis
  - a. Description of the organisation (name, location, mission)
  - b. Features of the organisation that relate directly and indirectly to HIVST- in terms of potential for distribution of kits, return of test kits and linkage to care and confirmatory testing
  - c. Potential impact of HIVST on the organisation 1) positive Vs negative
  - d. Willingness of the organisation to collaborate with STAR 2 and in which ways
3. For potential distribution points, the assessment will include
  - a. Accessibility (address, road, location)
  - b. Storage and safety

- c. Quality assurance
- d. Waste management (waste disposal system)

#### **Observations, in-depth interviews and focus-group discussions**

Observations will be conducted to observe the process of HIVST distribution and the interactions between staff distributing HIVST, the people and the general setting.

Observation checklists will be developed and utilized by qualitative research assistants to collect and document contextual activities happening at the distribution points, in the community and in qualitative cohort participants' homes/environments when interviews are conducted in these places, or if they visit the homes for any reason. IDIs will be conducted with purposefully selected participants to obtain their perspective on issues pertaining to HIVST distribution and to explore factors that influence access, acceptance, utilisation and linkage to confirmatory and prevention and care services. Focus groups discussions will be conducted with purposefully selected community members to obtain community perspectives on HIVST distribution including secondary distribution.

### **4.3. Quantitative methods**

#### **4.3.1 Process data**

Process data collected during distribution of HIVST kits by the SFH and Zambart distributors will be used. SFH has developed simple tools (Appendix 2) that distributors will use for all the distribution models. The information to be collected include age, sex, level of education, occupation, whether an individual accepts the test kit or not and the reasons for not accepting the test kit. In all the distribution models, this information will be collected using a simple paper-based questionnaire or register. The process measures collected for each of the five distribution models will include:

[figure not shown]
- 1) The number of HIVST kits offered through the five models of distribution, the number of HIVST kits accepted and the number of HIVST kits returned.
- 2) Proportion of individuals offered an HIVST who accept the offer, by model of distribution

#### **4.3.2 Secondary Distribution Cohorts**

For the two secondary distribution models, we will recruit two cohorts of individuals (one from ANC and one from HIV+ individuals attending HIV testing and treatment services) to collect data on outcomes of distribution over time (Figure 2 and 3 First, we will conduct an exit interview with consecutive HIV+ individuals (attending HIV testing and treatment services) and ANC attendees (HIV status irrelevant) to determine the proportion who accepted an offer of an HIVST for secondary distribution and determine factors associated with accepting an offer of HIVST for secondary distribution.

At the end of the exit questionnaire, individuals self-reporting that they accepted an offer of secondary distribution HIVST will be asked for permission to be followed-up within 1-month after the exit interview to measure use of the secondary distribution HIVST. We will also aim to

follow-up the intended user of the secondary distribution HIVST within approximately 3-months to measure self-reported use and linkage to care as reported by the intended users. A timeline specific to the secondary distribution cohorts is given in Figure 2.

**Figure 2: Schematic of the quantitative and qualitative cohort in ANC and ART models**

For the secondary distribution cohorts, we will measure individual- and couple-level factors associated with acceptability to the index patient and intended user including: sex, age, previous HIV testing history, newly diagnosed or previously undisclosed HIV, relationship of the distributor and intended user (including type of relationship, age differential, measures of equality and empowerment), history of gender based violence and clinic from which the Index was recruited (ANC or HIV testing and treatment services).

The primary outcome of the secondary distribution cohorts is the:

- 1) Proportion of index patients who accepted an offer of secondary distribution HIVST kit(s) who report that their sexual partner(s) used the HIVST kit,

Secondary outcomes are the:

- 1) Proportion of index patients accepting an offer of HIVST kit(s) for secondary distribution,
- 2) Proportion of index patients who accepted an offer of a secondary distribution HIVST kit(s) who report that their partner used the HIVST kit(s) and linked to prevention or care services within 1-month of distribution

- 3) Proportion of intended recipients who self-report a) having used an HIVST kit and b) having attended confirmatory HIV testing, or HIV prevention or HIV care services within 3-months of distribution.

**Figure 3. Timeline specific to the secondary distribution cohorts**

	2018												2019												
	May		Jun		Jul		Aug		Sep		Oct		Nov		Dec		Jan		Feb		Mar		Apr		
	May	Jun	Jul	Aug	Sep	Oct	Nov	Dec	Jan	Feb	Mar	Apr	May	Jun	Jul	Aug	Sep	Oct	Nov	Dec	Jan	Feb	Mar	Apr	May
Exit interview																									
IDI with 12 cohort participants																									
Analysis of exit interviews																									
Follow-up survey index patient																									
Follow-up IDI with 12 cohort participants																									
Questionnaire with intended user of HIVST																									
Analysis of follow-up surveys																									
Write up for dissemination & publication																									

#### 4.4 Economic methods for five models of distribution

##### 4.4.1 Economic evaluation

A comparative prospective economic evaluation of HIVST distribution models (Table 1) will be prospectively done from a societal perspective. Costs of HIVST will be compared with facility-based rapid blood finger prick HIV testing services.

##### 4.4.2 Cost analysis

Full provider and societal costs of each distribution model will be estimated using a top-down costing approach. Analysis of programmed expenditures, complemented by field observations, will allow estimated on costs by input and model. Field observations and monitoring will generate allocation factors across activities and shared resources as well as identifying associated economic costs of providing the intervention that are not solely borne by the project. Data sources will include financial records, procurement documents and patient records as well as interviews with distribution team. We will also calculate the costs of linkage to HIV prevention and care services by combining utilisation data reported in the quantitative cohort with unit costs which will be prospectively collected.

Direct medical and indirect user costs and willingness-to- pay (WTP) will be collected through questions asked on service utilisation costs in the case studies. The cost of the main comparator will be collated from the study done in STAR phase I [22]. In the base case, capital cost will be annualized using a 3% discount rate as used in similar studies [22-24]. Costing tools will be adapted from STAR phase II costing tools. We will collate information on process indicators from the M&E data such as numbers of kits distributed, number individuals self-tested, number referred for confirmatory test, number of individuals referred treatment and number starting treatment to obtain unit costs for each indicator.

##### 4.4.3 Cost-effectiveness analysis

The incremental cost-effectiveness of each additional distribution model, relative to the standard of care (facility-based finger HIV prick testing) will be estimated. An existing decision model developed in STAR phase I, estimating \$ per DALY averted of the STAR phase I HIVST distribution models will be extended to estimate the cost per DALY averted for the new HIVST

distribution models. The analysis will be undertaken by economists from Zambart with support from economists at LSHTM.

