**Table 1: Summary of HIVST distribution models**

Model	Description	Implementer
1 VMMC	VMMC mobilizers distribute HIVST to men interested in VMMC.	SFH
2 Facility-led and Community-led	The facility-led model will utilize existing clinics to distribute HIVST kits within specified departments of the facility and during outreach programs.  HIVST kits will be distributed using existing community structures such as shops of hubs (kanterbas) that are otherwise not directly linked to the health facilities. Communities will determine the best way to distribute the tests and manage all distribution activities.	SFH Zambart and MOH  SFH and Zambart
3 Workplace	Distribution of HIVST in targeted workplaces where HIV risk may be high (uniform/security professionals, truck drivers, taxi ranks etc.) and testing using routine finger-prick test is low or unsuccessful, HIVST distribution through peer educators or distribution agents.  Distribution will be done in a private room or outside in a tent. Workers will walk in at their own time to collect an HIVST. Process data will be collected using a self-administered questionnaire. There will be no individual tracking for linkage to care and treatment.	SFH
4 Secondary Distribution through ANC	This model is part of the facility-led HIVST distribution model, above. HIVST for secondary distribution will be offered to women attending ANC for their primary partners.	SFH and MOH
5 Secondary distribution through individuals who know their HIV	Trained lay counsellors for Zambart models and SFH and MOH staff for models implemented by SFH will distribute HIVST through individual HIV+ patients. The lay counsellors will offer HIVST kits to HIV positive individuals who self-report to: be in a discordant	Zambart, MOH and SFH

---

positive status	relationship; to have a partner with unknown HIV positive status or to have HIV negative partner who wishes to re-test.
-----------------	---

---

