## **8.2 HIVST procedures**

We are not requesting informed consent for individuals accepting HIVST kits because distribution of HIVST kits is now standard practice in Zambia. Multiple partners are providing test kits in the country including PEPFAR, MOH from Global Fund as well as the STAR

consortium. The national Virus Reference Laboratory is monitoring the quality of the test kits. Distribution will be conducted by MOH staff and staff of implementing partners who will be trained to adhere to national and international best practice for HTS, stressing that HIV testing is a voluntary process. HIVST distributors will be trained on provision of pre-test information, including how to perform the self-test, interpret results, and link to confirmatory testing, ART or VMMC services. Observations in communities and in health facilities will be explained to individuals who are being observed and they will have the opportunity to refuse observation. Written consent will not be requested as this would likely alter behaviour. Observation notes will never identify individuals.

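### Section 4.4.3 values the ANC and HIV-service models only against finger-prick testing, although the protocol elsewhere calls kit distribution routine, so the cost per DALY of adding these models may be understated

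*Protocol*

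**What the plan says.** Objective 7 in Section 2.2 covers four of the five models; VMMC is left out, and Table 2 marks it as already costed. The comparator is named in two places. Section 4.4.1: "Costs of HIVST will be compared with facility-based rapid blood finger prick HIV testing services". Section 4.4.3: "The incremental cost-effectiveness of each additional distribution model, relative to the standard of care (facility-based finger HIV prick testing) will be estimated". Section 4.4.2 takes the cost of what it calls the main comparator from a STAR phase I study of facility-based testing and names no second comparator.

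Other sections describe the setting differently. Section 8.2, explaining why no consent is sought for taking a kit, says that "distribution of HIVST kits is now standard practice in Zambia" and adds: "Multiple partners are providing test kits in the country including PEPFAR, MOH from Global Fund". Section 8.1 calls self-testing standard practice when it argues for a waiver of parental consent. Section 1.4 reports that HIVST has become routine delivery in Zambian health facilities.

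On how the models sit together, Table 1 says of the ANC model: "This model is part of the facility-led HIVST distribution model, above". Section 4.1 says that in each community "the facility-led model will be implemented in the public health facility and the community-led model will be implemented in all facility catchment areas". Appendix 1 places both secondary distribution models in public health facilities.

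**The concern.** The study is meant to guide early scale-up (Section 2.1) and the allocation of resources for HIVST (Section 1.4). Someone deciding whether to add ANC or HIV-service distribution, in a place where a facility already hands out kits and shops or hubs in the catchment area do the same, needs the extra cost and extra health gain over that situation.

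The planned ratio answers another question: what the model buys compared with finger-prick testing alone. If part of its effect would have come through kits already in circulation, the planned ratio still credits all of it to the model. The ratio does not react to overlap at all, so a secondary distribution model that adds little could show the same figure as one that adds much.

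**Working it through.** The protocol states no cost, effect, ratio or threshold, so there is no figure of its own to reproduce. The check compares the texts and then works out how the ratio depends on overlap.

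**1. The baseline.** Section 4.4.3 labels finger-prick testing the standard of care. Sections 1.4, 8.1 and 8.2 describe self-testing or kit distribution as routine or standard. A standard of care without HIVST does not describe that setting, and no section explains the difference.

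**2. Where the baseline matters.**
- *ANC model:* part of the facility-led model (Table 1). Appendix 1 puts facility-led distribution in maternal and child health departments among others.
- *HIV-service model:* same public facilities, with community-led distribution in their catchment areas. The community-led audience is the targeted population above 16 years (Appendix 1), which can include the partners whom both secondary models aim to reach.
- *Facility-led and community-led:* one combined model (model 2 in Table 1), so their co-location is not overlap between two listed models.
- *Workplace:* sites may lie outside the five communities (Section 4.1).
- *VMMC:* not costed.

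The point therefore concerns models 4 and 5.

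**3. Is overlap handled already?** Section 4.4.2 plans allocation factors, but these divide shared resources on the cost side. The process indicators it lists are counts (kits distributed, people self-tested, people referred, people starting treatment). No step is stated that removes tests which another running model would have produced.

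**4. How the ratio moves.** Let a model cost C and avert E DALYs against finger-prick testing, so the planned ratio is R = C/E. Let o be the share of E that would occur anyway through kits already distributed. Let s be the proportional cost offset: displaced kits save C·o·s. Against current practice:

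- extra effect = E(1 - o)
- extra cost = C(1 - o·s)
- ratio = R × (1 - o·s)/(1 - o)

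All values of o and s below are assumptions. The entries are multipliers of the planned ratio.

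| Overlap o | s = 0 | s = 25% | s = 100% |
|---|---|---|---|
| 0% | 1.00 | 1.00 | 1.00 |
| 25% | 1.33 | 1.25 | 1.00 |
| 50% | 2.00 | 1.75 | 1.00 |
| 75% | 4.00 | 3.25 | 1.00 |
| 90% | 10.00 | 7.75 | 1.00 |

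Worked entry: o = 50%, s = 25% gives (1 - 0.125)/(1 - 0.50) = 0.875/0.50 = 1.75.

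With any overlap and s below 1 the multiplier exceeds 1. With o = 0 or s = 1 it equals 1. If displaced distribution cost more per unit of effect than the added model (s above 1), it would fall below 1. So the direction is likely but not certain.

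**5. What the study collects on o.** The exit interview asks women attending ANC whether they have ever used a self-test (Appendix 3, item H_HIVCT 3). The intended-user questionnaire asks about self-test use before the partner's kit (Section 3, third item). The second bears directly on the people whom the secondary models try to reach.

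**The case against.** The strongest reply has five parts.

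*The standard-practice statements are ethics text.* Sections 8.1 and 8.2 justify consent arrangements and say nothing about coverage. Section 1.3 says that the country operational framework is still being developed, and Section 2.1 speaks of early scale-up. This weakens any claim that overlap is large. It does not remove the conflict of labels, because Section 1.4 makes a similar statement outside the ethics text.

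*Finger-prick testing is a legitimate comparator.* Facility-led distribution is itself under evaluation, so a baseline that contains it could not evaluate it. This stands, and it is why the finger-prick result should stay. It does not cover the ANC and HIV-service models, for which facility- and community-led distribution is a background and not the thing being valued.

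*Sharing a place is not sharing health gain.* The ANC model aims at male partners who have not come to the clinic, while facility-led clients test on site. This stands: overlap of effect is possible but undocumented.

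*Dominance.* A reader might infer that all costed models should be ranked by cost, dominated ones removed, and that the plan can make a dominated model look good. The documents do not support that. Such an ordering is for mutually exclusive options in one population; these models reach different people, can be funded together, and one is nested in another.

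*Secondary comparators belong in an economic analysis plan.* Silence on a second comparator would indeed be no finding. Here the protocol names the comparator, calls it the standard of care and describes current practice differently elsewhere. Section 4.4.1 does call the evaluation comparative, but names only the finger-prick comparison.

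**Conclusion.** The concern holds in a limited form. The protocol is inconsistent about what the standard of care contains, and for the two secondary distribution models its only stated comparator does not give the value of adding the model where kits are already distributed. For those models the planned ratio may understate the cost per DALY.

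The size is unknown. The multipliers of 1.25 to 4 for overlaps of 25% to 75% (cost offset 0 to 25%) rest wholly on assumed inputs. A reader might infer that every model's ratio is too low, by a factor of that order. The documents do not show this: they give no overlap figure, they do not cost VMMC, they allow workplaces outside the communities, and they treat facility- and community-led distribution as one model.

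The point affects a named economic objective and the policy reading of it. The primary outcome of the cohorts is untouched.

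**What to change.** 1. Reconcile the standard-of-care wording in Section 4.4.3 with Sections 1.4, 8.1 and 8.2, stating what current practice at the study sites is taken to include.
2. Keep finger-prick testing as the reference comparator for all costed models.
3. For the ANC and HIV-service models, add to Section 4.4.3 an incremental comparison with current practice that includes the facility- and community-led HIVST model. Vary the effect overlap over a stated range and state the assumed cost offset. Use the prior self-test questions in Appendix 3 to inform the range. They measure past use, not what would have happened without the kit. Intended users are also approached only when the index patient reports that the kit was used (Section 5.2), so they guide the range and do not fix it.
4. Apply dominance ordering only to models or mixes that are true alternatives for the same population.

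The cost is extra runs of a decision model already being extended, an explicit overlap assumption, and possibly less favourable ratios. No new data collection is needed.
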